## **PROTOCOL**

## **Background:**

Diabetes Mellitus is a major public health problem worldwide in the United States. Chronic wounds are a debilitating condition associated with Diabetes. An estimated excess of US\$25 billion is spent annually on treatment of chronic wounds and the burden is rapidly growing due to increasing health care costs, an aging population and a sharp rise in the incidence of diabetes and obesity worldwide.

The clinical use of oxygen to promote wound healing began in the 1960s with the administration of systemic hyperbaric oxygen (HBO) to treat wounds. Today, HBO therapy is approved by the Center for Medicare and Medicaid Services (CMS) in the US to treat specific ulcerations. Although HBO is a clearly promising mode of wound therapy, it requires extensive facilities that may not be available to all patients. Moreover, many wound patients cannot tolerate the systemic HBO therapy side effects.

The approach to topically oxygenate wounds using a variety of approaches is distinct from the conventional HBO therapy in numerous ways. For example, topical approaches do not involve high pressure, are not systemic in nature and, therefore, do not pose the uncommon risk of systemic oxygen toxicity. Our researchers among others have extensively demonstrated that wounds may benefit when oxygenated topically and is supported by the published work. Topical Oxygen therapy, defined as oxygen applied topically to a local area, was first used for treatment of pressure sores and skin ulcers three decades ago. By creating an environment of hyperoxia only in the target region it was hypothesized that systemic complications could be minimized while achieving the desirable local wound effects. Oxygen at a pressure of 1.03 to 1.04 atmospheres absolute was allowed to flow over open wounds enclosed by specially constructed boot-like devices for the lower extremity and contoured cup units for sacral lesions. Heng et al reported increased healing rates and increased granulation tissue formation in leg ulcers of patients from a controlled study of 6 men receiving hydrogen peroxide wet-to-dry dressings plus Topical Oxygen therapy delivered by disposable polyethylene bags compared to 5 controls receiving hydrogen peroxide wet-to-dry dressings alone. The authors proposed that the mode of action of Topical Oxygen therapy was direct diffusion of oxygen into the open wound bed, wound fluid, surrounding tissue fluid, and proliferating epidermal cells and fibroblasts.

## **Objective:**

To observe the effect of application of topically administered oxygen on risk adjusted

outcomes (healing rates, rate of amputations, post-treatment health complications, cost of care) in 40 diabetic patients with chronic wounds.

This is a pilot study which is intended to collect data to calculate an adequate sample size for a larger registered clinical trial. Eleven subjects were enrolled at The Ohio State University; we intend to enroll 29 more subjects at Indiana University. Due to the small sample size this study will primarily be a feasibility study that will attempt to measure and evaluate differences in the relative theoretical costs of the intervention of topical oxygen therapy on this population and subsequently compare outcomes in areas such as overall health improvements and cost effectiveness.

Primary Outcome: Wound healing rates 16 weeks post treatment as compared to the baseline visit.

Secondary Outcomes: Rate of amputations, post-treatment wound complications such as wound infection, QoL (SF-36), cost of care 16 weeks post treatment as compared to the baseline visit.

For details of outcomes see **STUDY ASSESSMENTS AND PROCEDURES**

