**Table-1: Study Timeline**

Week(s)	0 (Visit 1)	1-3	4 (Visit 2) (+/-2 weeks)	5-7	8 (Visit 3) (+/-2 weeks)	9-11	12 (Visit 4) (+/-2 weeks)	13-15	16 (Visit 5) (+/-2 weeks)
Study Visit	✓		✓		✓		✓		✓
Digital Imaging	✓		✓		✓		✓		✓
Topical oxygen or SoC treatment administered at home	✓	✓	✓	✓	✓	✓	✓	✓	✓

**Study Population:** 40 chronic wound patients with diabetes will be recruited based on study inclusion and exclusion criteria by the research personnel. Patients will be randomized into one of the 2 patient groups: the topical oxygen group and the other half randomized into the comparison group.

A proportionate stratified random permuted block design will be used to generate random assignments to the two groups. The stratification will be based on the proportion of patients expected to be seen at a wound center with Wagner grade 1, 2, or 3. This method will ensure balance across the groups and strata and will also account for the difference in the severity over the course of the study period. The biostatistician at the Center for Outcomes Research in Surgery will prepare the master randomization assignment list. The clinical research coordinator will administer randomization using REDCap.

**Blinding.** This is an open label trial. To reduce bias, the personnel involved in evaluating study outcomes will be blinded to treatment group. The standard of care will be provided by their providers at CWC as part of their routine wound care and will not be blinded to treatment group.

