**Statistical Analysis Plan:**

**Sample size.** Although the main objective of this pilot trial is not to detect the significant difference between the two study groups, rather to provide preliminary data for the design of future trial, with sample size of n=40 (n=20 in each arm) could also provide at least 80% power to detect superiority of the TO+SoC treatment success rate (50%) vs. SoC (10%) based on a one-sided Fisher's Exact test at a significance level of 0.05.

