## Statistical analysis.

Univariate analysis will be done using frequencies, mean (SD), median (IQR) to describe the patient cohort. Cumulative incidence of wound healing rates 16 weeks post treatment with 95% confidence interval around the risk estimate will be computed for the two groups (SoC and TO+SoC). Bivariate logistic regression will be used to report the odds of wound healing among those with TO+SoC compared to SoC only. Bivariate analysis to compare secondary outcomes between the groups will be done using Chi-square or Fisher's exact tests for categorical variables and t-tests or Mann-Whitney tests for continuous variables (e.g. QoL ratings from SF-36, costs).

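### Patients from two sites are pooled, but site is neither a randomisation stratum nor an analysis term, so a chance imbalance by site would pass uncorrected into the healing and cost comparisons

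*Combined protocol and SAP*

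**What the plan says.** The Objective gives the make-up of the sample: "Eleven subjects were enrolled at The Ohio State University; we intend to enroll 29 more subjects at Indiana University". The Sample size paragraph of the Statistical Analysis Plan uses both groups together: "with sample size of n=40 (n=20 in each arm) could also provide at least 80% power".

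The Study Population text below Table-1 describes the allocation: "A proportionate stratified random permuted block design will be used to generate random assignments to the two groups". The only stratification factor is Wagner grade: "The stratification will be based on the proportion of patients expected to be seen at a wound center with Wagner grade" 1, 2 or 3. Site is not named.

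Under Statistical analysis, "Bivariate logistic regression will be used to report the odds of wound healing among those with TO+SoC compared to SoC only". Secondary outcomes, with costs given as an example, are compared by two-group tests. No covariate enters either analysis, yet the Objective describes the outcomes, cost of care included, as risk-adjusted.

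The Standard of Care Therapy section describes care at the Comprehensive Wound Center. It leaves changes to practice guidelines and provider discretion, and infection treatment to local guidelines. The Study Procedure section places that center at the second site. The Cost of care item takes costs from that center's billing and gives no source for the 11 first-site patients. The documents do not say how those 11 were randomised or how they divide between arms.

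**The concern.** The two groups of patients come from different institutions and different enrolment periods. If healing or cost differs between sites and the arms are uneven within site, part of the site difference appears as a treatment difference, and nothing in the planned analysis removes it.

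Eleven patients cannot divide equally, so some imbalance at the first site is certain unless its weight in the two arms is adjusted for. The cost comparison deserves most attention. The Objective makes relative cost a main purpose of the study, and cost is where the data source for the first site is undocumented. The pilot is also meant to supply planning figures for a larger trial, and a pooled rate would hide any difference between sites in those figures.

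**Working it through.** **The plan's own power figure.** Inputs from the Sample size paragraph: 20 per arm, and "treatment success rate (50%) vs. SoC (10%) based on a one-sided Fisher's Exact test at a significance level of 0.05". Summing the two binomial distributions over every table that the test rejects gives exact power 0.837, so the stated minimum of 80% is reproduced. It depends on pooling: with the 29 second-site patients alone (15:14 or 14:15), the same calculation gives about 0.69.

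**Shift in the crude result.** Let the first-site patients split a:b between the arms, with a + b = 11 and 20 per arm overall. Let Δ be the difference between sites in healing (or in mean cost), the same in both arms. Then

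shift in arm difference = (a/20 − b/20) × Δ = ((a − b)/20) × Δ.

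The documents give no Δ. The range of 10 to 30 points for healing is an assumption.

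| Split of the 11 | (a − b)/20 | Δ = 10 | Δ = 20 | Δ = 30 |
|---|---|---|---|---|
| 6:5 | 1/20 = 5% | 0.5 | 1.0 | 1.5 |
| 7:4 | 3/20 = 15% | 1.5 | 3.0 | 4.5 |
| 8:3 | 5/20 = 25% | 2.5 | 5.0 | 7.5 |

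The last three columns are percentage points of healing. The second column is also the share of any site difference in mean cost that enters the arm contrast.

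**How likely the splits are.** Block size is not stated. Simulating permuted blocks in three Wagner strata, and assuming that this scheme covered the 11, gives, in either direction:

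| Assumed block size | 7:4 or worse | 8:3 or worse |
|---|---|---|
| 2 | about 6% | does not occur |
| 4 | about 18% | under 1% |
| 6 | about 30% | about 3 to 4% |

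The usual split is therefore 6:5. If blocking is ignored and 20 of the 40 are drawn at random for one arm (hypergeometric), the figures are 48% and 16%.

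**Bias and error rate over repeated randomisation.** With a common healing rate of 30%, site differences of 0 to 30 points and 20,000 simulated trials per setting, the mean crude difference lay within 0.002 of zero. The one-sided error of the pooled Fisher test was about 0.02 to 0.03, below 0.05.

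**Price of adjusting for site.** At 50% against 10%, a site-stratified exact test has power of about 0.82 with no site difference (0.83 if randomisation is also stratified by site), against 0.84 pooled. With a site difference of 30 points it has about 0.87. The simulated standard deviation of the Mantel-Haenszel risk difference is 0.147 against 0.145 for the crude one when sites do not differ, and slightly below the crude one when they do.

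**Why a site covariate and not site-centred costs.** Suppose the true cost difference between arms is τ at both sites. Subtracting each site's mean and then comparing arm means gives τ × (w₁ + w₂)/10, where w is the product of the two arm sizes at a site divided by the site total.
- At 7:4: w₁ = 7 × 4/11 = 2.55 and w₂ = 13 × 16/29 = 7.17, so the result is 0.97τ, a shrinkage of about 3%.
- At 8:3: w₁ = 8 × 3/11 = 2.18 and w₂ = 12 × 17/29 = 7.03, so the result is 0.92τ, a shrinkage of about 8%.

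A regression of cost on arm and site does not shrink τ.

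**The case against.** A reader might infer that the planned comparison is biased or that its error rate is inflated. The documents do not support this. Allocation is described as random to two equal groups, and under such allocation the crude comparison is unbiased on average and the error rate is held. What remains is imbalance, in the one trial that will be run, on a factor that was left out.

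A reader might also take a 7:4 split as close to a coin-flip. That holds only if the permuted blocks are ignored; with blocks it is the less common case, and 8:3 is rare.

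Third, it is tempting to say that the sites bill differently. No passage says so, and no passage shows that first-site costs enter the comparison at all. The documented gap is narrower: the only named source is the second site's billing. Nor is care simply left to each site. The plan lists common procedures, ties changes to guidelines, and says changes in care will be recorded and considered in the analysis. That safeguard gives no method and does not mention site.

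Finally, this is a pilot whose main aim is not to detect a difference, and the healing shift is small beside 40 points. This stands and limits the weight of the point. It does not remove it, because the adjustment costs almost nothing and the missing facts about the 11 can only be supplied by the study team.

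**Conclusion.** The point holds as a minor one. Two sites are pooled, and site appears in neither the strata nor the analysis, despite an objective framed as risk-adjusted. If all 40 are randomised 1:1, the consequence is chance imbalance: most likely a shift of 0.5 to 1.5 points in healing, and less often 1.5 to 4.5. These figures rest on assumed site differences of 10 to 30 points, equal arms of 20, and the stated blocking having covered the 11. For cost, the share passed into the arm contrast is 5% at 6:5, 15% at 7:4 and 25% at 8:3, whatever the site difference proves to be.

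One matter stays open. If the 11 were allocated in a different arm ratio from that used at the second site, the confounding would not be due to chance alone. The documents neither show nor rule this out.

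**What to change.** In the Statistical analysis section:
- Beside the crude result, give the site-stratified Mantel-Haenszel risk difference for healing with its 95% interval.
- Compare mean costs with site as a covariate, not by centring costs by site.
- Report healing and cost by site and arm.
- State how the 11 first-site patients were randomised, how they split by arm, and the source of their costs.

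This is a change of wording in the analysis plan, best made before results by arm are seen. Its downside is a slightly wider interval if sites do not differ; the stated 80% power is kept.

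Starting new blocks for the 29 is optional and not part of this fix. It would change the randomisation list and the REDCap set-up, unless a new list is already intended, on which the documents are silent. It also makes overall imbalance more likely: with equal strata, the chance of an arm difference of 4 or more among the 40 rises from about 4% to 16% with an assumed block size of 4, and from about 9% to 27% with 6.

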### **Study design:**

The proposed study is pilot/feasibility study, in which the effectiveness of topical oxygen (100%) administered four days per week, for 16 weeks, for the treatment of diabetic foot ulcer (DFU) or chronic wound will be compared with standard of care (SoC) treatment.

- Subjects will be randomized into one of the two patient groups: **Group 1** will only receive standard of care (SoC) treatment.

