**c. At Home Treatments (4 consecutive days per week, treatment group only):**

1. A trained, approved study personnel will first attend the subjects' home

or extended care facility to provide the supplies, instruct and give support on how to use the TO device (performed solely for research purposes only)

- The approved personnel will teach the subject how to use the TO device and instruct the subject to complete this treatment 4 consecutive days a week, followed by 3 days of no treatment.
- The treatment will begin with the study personnel during the first home care (on site) visit:
  - The 90 minute therapy includes the removal of the ulcer dressing, the ulcer is cleansed/ moistened and the extremity is inserted into an FDA cleared single use oxygen delivery device (GWR Medical, Inc. Chadds Ford, PA).
  - If necessary, a band around the wound is prepared for fixation of the Topical Oxygen device by shaving the limb circumferentially over approximately a 10cm band (done at initial treatment and as needed subsequently).
  - After the 90 minutes, the single use device will be removed and disposed of.
    - Wounds will be treated with standard care at the physician's discretion and diabetic foot ulcers (DFUs) will be administered with a standardized offloading boot to distribute pressure across the entire surface of the foot, specifically removing pressure from the ulcer site per SoC (a non-antimicrobial boot).

2. Trained study personnel will be assigned for the subject, who will receive at home support for the treatment. The study personnel will make weekly phone calls to the subject to check on progress with TO therapy; personnel may go to the subject's home/ care facility on as as-needed basis if the subject is having difficulty with the treatment.
3. Subjects will be given a data collection log (diary) to document the date, time and that the treatment was completed. This will be checked at each study visit and will be collected at their next follow-up visit for compliance.
4. Treatments will continue until the ulcer has closed, an amputation (above or below knee) has been performed, the ulcer's healing has stalled (defined that the size of the wound is unchanged or increased in size in the past 2 visits) or 16 weeks of therapy has been completed.

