d. **SoC group only-** Patients will receive Standard of Care for their wound per the study physician's discretion. There will be no at home treatments for this study population but they will be asked to return for follow-up visits at 4, 8, 12, and 16 weeks following their baseline visit.

1. Subjects will be given a data collection log (diary) to document information about the SoC including wound dressing intact, offloading boot being used (for DFU's), the date, and the subject's initials. This will be checked at each study visit and will be collected at their next follow-up visit for compliance.
2. SoC will continue until the ulcer has closed, an amputation (above or below knee) has been performed, or the ulcer's healing has stalled (defined that the size of the wound is unchanged or increased in size in the past 2 visits).

All wounds for both groups will be treated with standard care and will be administered with a standardized offloading boot that distributes the pressure across the entire surface of the foot, specifically removing pressure from the ulcer site will be utilized (a non-antimicrobial boot). Offloading boots are standard of care for these wounds and will not be provided by the study.

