#### **Week 16 (FSV) (+/- 2 weeks)/ Follow-up:**

Once the patient's ulcer has completely healed or the 16 weeks of treatment ends, the patient will return for their final study visit.

- If complete healing is achieved in less than 16 weeks, a follow-up visit will be scheduled at 16 weeks after enrollment.
  - Patients will be instructed to contact the study Physician should the ulcer recur.
  - The initially assigned oxygen treatments will be stopped at this time.
- Digital imaging of the ulcer to measure the response to therapy
- Quality of life questionnaire (SF-36) will be administered to all patients at 16 weeks.
- If the wound has not healed in 16 weeks, the wound is assessed as to its recent response to treatment.
  - Wounds, which have decreased less than 10% in wound surface area during the preceding 4 weeks, are designated as "Quiescent". Quiescent wounds are considered to be non-responders.

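### The primary outcome and cost are set 16 weeks after treatment, but treatment runs to week 16 and so does the last visit: the time point and its origin need restating

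*Combined protocol and SAP*

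**What the plan says.** **Time point of the outcomes.** The Objective section gives "Primary Outcome: Wound healing rates 16 weeks post treatment as compared to the baseline visit". Its list of secondary outcomes ends with "cost of care 16 weeks post treatment as compared to the baseline visit", and the same section labels health and wound complications as post-treatment. The Statistical analysis section plans "Cumulative incidence of wound healing rates 16 weeks post treatment with 95% confidence interval around the risk estimate" for each group.

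**Length of treatment.** Under Study design, oxygen is "administered four days per week, for 16 weeks". Under At Home Treatments it ends at closure, amputation or stalled healing, "or 16 weeks of therapy has been completed". For the other arm, the SoC-only item says "SoC will continue until the ulcer has closed, an amputation (above or below knee) has been performed, or the ulcer's healing has stalled" and states no 16-week limit. The Standard of Care Therapy section applies those procedures for as long as the patient is in the study.

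**Visits.** Table 1 ends with Visit 5 at week 16, with a window of 2 weeks either side, and still ticks treatment in that column. The Week 16 section says "Once the patient's ulcer has completely healed or the 16 weeks of treatment ends, the patient will return for their final study visit". It then gives patients who heal early a visit 16 weeks from enrolment, not from the end of treatment.

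**Measurement and clock.** Study Assessments and Procedures, item a, compares wound area at baseline with wound area at the last visit. The item on the 4, 8 and 12 week visits times oxygen-arm follow-up from the day oxygen is first given. The SoC-only item times it from the baseline visit.

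**The concern.** The time point in the outcome definition and in the analysis plan does not exist in the schedule. It appears for the primary outcome, for the secondary outcomes and in the analysis text, so it is not a single slip.

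Two things are at stake. First, someone who reads only the outcome statement would take the result as healing that has lasted 16 weeks beyond the end of oxygen. The trial cannot show that, and as a pilot meant to size a larger trial it would pass the ambiguity on. Second, any measure defined from the end of treatment depends on when treatment ended. That moment is driven by the patient's course in the oxygen arm and is not consistently defined in the SoC arm. The analyst needs one time point and one origin that mean the same thing in both arms.

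**Working it through.** **The plan's own figure first.** Inputs from the Sample size paragraph: 20 per arm, success 50% against 10%, one-sided Fisher's exact test, significance level 0.05. Power is the sum, over all pairs (x, y) with one-sided Fisher p at or below 0.05, of Bin(x; 20, 0.50) × Bin(y; 20, 0.10). Exact enumeration gives 0.837, which agrees with the claim of at least 80%. The calculation contains no time point, so the timing problem does not alter it.

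**Follow-up after treatment.** Inputs: the last visit at week 16, at the latest week 18 (Table 1); the stopping week s, at most 16 (Study design; At Home Treatments). Both are counted here from the start of treatment.

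Follow-up after treatment = visit week − s.

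| Treatment stops at week | Visit at week 16 | Visit at week 18 |
|---|---|---|
| 16 | 16 − 16 = 0 | 18 − 16 = 2 |
| 12 | 16 − 12 = 4 | 18 − 12 = 6 |
| 8 | 16 − 8 = 8 | 18 − 8 = 10 |
| 4 | 16 − 4 = 12 | 18 − 4 = 14 |
| 2 | 16 − 2 = 14 | 18 − 2 = 16 |

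A full-course patient would need a visit at week 16 + 16 = 32. Using the whole window, a patient can reach 16 weeks after treatment only if s is at most 18 − 16 = 2. The first visit after baseline is due at week 4, or week 2 at the earliest within its window. Almost no patient can therefore have the outcome as worded.

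**End of treatment in the SoC arm.** One section runs SoC for the whole of participation. Another ends it at closure, amputation or stalling, without a 16-week limit. For a patient with none of these events, neither text gives a date from which to count 16 weeks.

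**The two clocks.** Randomisation takes place at the initial visit. Let d be the number of weeks from that visit to the first oxygen treatment; the documents give no value for d. The nominal week-16 visit then falls 16 + d weeks after randomisation in the oxygen arm and 16 weeks after it in the SoC arm. The two agree only if d = 0. Any delay gives the oxygen arm d more weeks in which to heal before assessment.

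**Cost.** The Objective section sets cost against the baseline visit. Cost accrues over a period, and the Cost of care item names billing as the source but states no period. The Statistical analysis section compares costs between the groups, which is a different contrast.

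**The case against.** The strongest reply is that the intended time point can be recovered. The Objective section sends the reader to the assessment section, where healing is measured from baseline to the last visit. The SF-36 is given at 16 weeks, early healers return 16 weeks from enrolment, and nothing points to week 32. On that reading the phrase is loose wording for 16 weeks from the start, and healing can be assessed in everyone who attends Visit 5. This is the likelier intent, and it stands.

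It does not settle the matter. The assessment item covers healing only, not complications or cost. The last visit is itself unclear for early healers, because the Week 16 section triggers it at healing and then adds a week-16 visit. The analysis text keeps the conflicting phrase.

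Three stronger readings are tempting and are not supported:

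- A reader might infer that the outcome is observed only in patients who stop early. Taken literally, it is missing in nearly all of them too: a stop at week 8 leaves 8 weeks, or 10 with the window. Taken as the assessment section has it, it is observed in everyone who attends.
- A reader might apply the design rates, 0.5 × 20 = 10 against 0.1 × 20 = 2, and infer a five-fold imbalance in who can have a post-treatment complication. The plan gives success rates, not closure times, and stops for stalling or amputation could narrow or reverse the ratio. Complications are also noted at the week 4, 8 and 12 visits in both arms, and no text limits the count to events after treatment.
- A reader might infer that cost cannot be analysed. The between-group comparison is already planned; what needs correcting is the baseline contrast and the missing period.

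**Conclusion.** The inconsistency is real and lies in the definition of the primary outcome. A full-course patient has 0 to 2 weeks of follow-up after treatment against the 16 stated, and reaching 16 requires a stop by week 2 together with a visit at week 18. These figures assume that the Table 1 windows are kept and that weeks are counted from the start of treatment. In addition, the end of treatment is not consistently defined in the SoC arm, and the visit clocks differ by the unreported delay d.

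The data for a week-16 analysis will exist for all who attend Visit 5, and the power claim is untouched. The trial is therefore not left without a measurable primary outcome. What is wrong is the stated time point, its origin, and the conclusion about durability that a reader would draw. It should be corrected before analysis, and the correction is mostly one of wording.

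**What to change.** 1. In the Objective and Statistical analysis sections, replace the time point with *at the week-16 visit*, consistent with Table 1, the Week 16 section and assessment item a. State which visit counts as the last one for a patient who heals early.
2. State one time origin for both arms, such as randomisation, and align the oxygen-arm visit timing and the SoC-only item with it.
3. Delete the post-treatment label. Count complications, infections, amputations and cumulative cost from that origin to week 16 in both arms, whether or not treatment has stopped. The Compliance section allows subjects to be removed from the study, so say whether their data to week 16 are still collected.
4. Drop the baseline contrast for cost and keep the between-group comparison already planned.
5. State that the trial gives week-16 results and does not address durability after oxygen stops. If outcomes after treatment are truly wanted, the schedule needs a visit for them and the SoC arm needs a defined starting point.

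**Cost.** Items 1, 4 and 5 are wording only. Item 2 changes oxygen-arm visit timing slightly: with an origin at randomisation, a patient who starts oxygen d weeks later has had at most 16 − d weeks of it at the nominal visit. Item 3 adds no visits, but may mean continuing to collect data on patients who would otherwise be removed. The claim becomes narrower, and sample size and power do not change.
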